### Treatment of inclusion and randomization errors

For ITT analyses, all children will be analyzed according to the treatment group to which they were randomized. For CACE analyses, children who did not attend all treatment follow-up visits will be considered as “non-adherent.” Ineligible children who were erroneously enrolled will be handled as a protocol violation and will be removed from the study, and from the analysis. Ineligibility is defined above in the section entitled “Study Eligibility and Recruitment.”

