## Study eligibility and recruitment

### Main trial

The population for this study will be children 6-59 months old with MAM or uncomplicated SAM presenting to the study facilities. MAM will be defined as mid upper arm circumference (MUAC)  $\geq 11.5$  and  $< 12.5$  cm, or weight-for-length/height z-score (WLZ/WHZ)  $\geq -3$  and  $< -2$  and absence of bilateral pitting edema. Uncomplicated SAM (i.e., cases of SAM that are eligible for ambulatory treatment) will be defined by all the following criteria: (i) MUAC  $< 11.5$  cm or WLZ/WHZ  $< -3$ , (ii) no clinical complications, (iii) absence of bilateral pitting edema, and (iv) child passes the appetite test (the child eats at least the amount of RUTF required for passing the appetite test as per Burkina Faso national guidelines (4)).

The inclusion criteria for MAM ambulatory treatment are:

- Age 6-59 months
- $11.5 \text{ cm} \leq \text{MUAC} < 12.5 \text{ cm}$ , or  $-3 \leq \text{WLZ/WHZ} < -2$
- Absence of clinical complications
- Absence of bilateral pitting edema

- Pass the appetite test
- Accompanied by caregiver or legal guardian
- Caregiver or legal guardian consents to participate

The inclusion criteria for SAM ambulatory treatment are:

- Age 6-59 months
- MUAC < 11.5 cm, or WLZ/WHZ < -3
- Absence of clinical complications
- Absence of bilateral pitting edema
- Pass the appetite test
- Accompanied by caregiver or legal guardian
- Caregiver or legal guardian consents to participate

The exclusion criteria for MAM or SAM ambulatory treatment are therefore:

- Acute malnutrition requiring hospitalization (presence of clinical complications, failure to pass the appetite test, or presence of bilateral pitting edema)
- Known allergy to any of the ingredients in the RUTF products
- Already enrolled in MAM or SAM ambulatory treatment program
- Presence of physical abnormalities that make measurement of anthropometry impossible
- Caregiver has intention to move out of the study area within the next 6 months

Children will be screened for eligibility upon presentation at the study health centers, and will be determined to be eligible upon diagnosis with uncomplicated MAM or SAM.

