#### Method of treatment assignment/randomization

A statistician who is not part of the research team will generate a randomization scheme for the allocation of the 3 supplements. Each unique randomization number is randomly allocated to 1 of 9 letter codes (e.g., A, E, I, Z, K, T, N, E, S)—3 letters for the SMS-RUTF supplement, 3 letters for the S-RUTF supplement and 3 letters for the standard RUTF (control group)—using a computer program in blocks of 45. Without the investigators' knowledge, the producers will be informed which letters to print on the package of each supplement. Information regarding the assignment of the letter codes to the intervention and control supplements will be stored electronically by the director of Nutrition, Diets and Health unit of IFPRI, inaccessible by the investigators, until analysis is completed.

Eligible children will be randomly assigned to one of the three study groups at study inclusion. The study staff will open the sealed envelope corresponding to the next sequential participant identification number in the presence of an eligible mother-child pair (in order of arrival) and will provide them with the RUTF supplement according to the letter code. The participant's number, as well as the letter code, will be recorded on the study participant's card, their medical records, and scanned into the electronic data capture system.

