## Analysis frame

Our primary analysis frame will be intention-to-treat (ITT). ITT groups will be defined by the randomization assignment to which participants are allocated; that is, all participants will be included in the analysis based on the treatment group to which they were randomized.

However, ITT analyses can bias effect sizes toward the null, spuriously demonstrating non-inferiority, because non-compliance diminishes any treatment effects (30). Despite this, ITT is still the recommended approach for non-inferiority trials (31). To mitigate this concern, we will conduct a secondary analysis in which we repeat all analyses with a Complier Average Causal Effects (CACE) approach. CACE analyses adjust for any differences between children who adhere vs do not adhere in characteristics that may influence outcomes, thus mitigating concerns of confounding. CACE analyses are also useful for superiority analyses, as these results can distinguish between the effects of the interventions themselves, and effects of the adherence to the interventions. Both ITT and CACE results will be presented. This is summarized in Table 5.

Adherence will be defined as attendance at all treatment visits. The characteristics to be considered for adjustment and the decision rules to determine whether adjustment will be made will be the same as described in the next section below.

*Table 5. Analysis approaches and sensitivity analyses by type*

Analysis type	Primary analysis	Secondary analysis	Sensitivity analyses
Non-inferiority	ITT	CACE	Exclusion of children who received both study products and standard of care products during treatment course
Superiority	ITT	CACE	Exclusion of children who received both study products and standard of care products during treatment course

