#### Interim analyses and data monitoring

No interim analyses will be done. Adverse events (AEs) and severe adverse events (SAEs) will be evaluated at every follow up visit during treatment (weekly for children with SAM and bi-weekly for children with MAM), and will be addressed and reported as per the study Standard Operating Procedures (SOPs).

A Data Safety and Monitoring Board (DSMB) will be convened prior to enrollment, who will monitor study progress and participant safety (including adverse events monitoring). Data reports will be prepared for the DSMB reporting the following:

- Study accrual profile and recruitment numbers by month
- Baseline characteristics
- Protocol violations
- Recovery and relapse rates
- Treatment outcomes
- (Serious) adverse events

The above data will be pooled across sites, blinded, and stratified by MAM vs SAM. All data will retain blinding at all times. No closed session (unblinded) reports will be done. No statistical testing will be done on any data reported to the DSMB; only descriptive data will be reported. A shell table depicting the outcome and adverse event summaries that will be sent to the DSMB for monitoring is depicted in Table 7. These monitoring reports will be sent to the DSMB prior to the DSMB meetings. The DSMB will meet after approximately 300 SAM children have treatment outcomes, or at the call of the DSMB chair or study investigators.

Table 7. Shell table of outcome and safety data to be monitored by DSMB

		MAM			SAM		
		Arm 1	Arm 2	Arm 3	Arm 1	Arm 2	Arm 3
Treatment outcomes							
		N with outcome data available =	N with outcome data available =	N with outcome data available =	N with outcome data available =	N with outcome data available =	N with outcome data available =
Recovered from treatment							
Death							
Default							
Non-response							
Referral							
Transfer							
Post-discharge outcomes							
		N with $\geq 1$ post-discharge visit =	N with $\geq 1$ post-discharge visit =	N with $\geq 1$ - post-discharge visit =	N with $\geq 1$ post-discharge visit =	N with $\geq 1$ post-discharge visit =	N with $\geq 1$ post-discharge visit =
		N of follow up visits =	N of follow up visits =	N of follow up visits =	N of follow up visits =	N of follow up visits =	N of follow up visits =
Relapse within 3 months							
Adverse event data*							

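### The SAP removes wrongly enrolled children from an analysis it calls intention-to-treat, sets no safeguards on that judgement, and does not say whether they stay in safety reporting

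*SAP*

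**What the plan says.** Under Analysis frame, the SAP names ITT as primary and states that "all participants will be included in the analysis based on the treatment group to which they were randomized". The section Treatment of inclusion and randomization errors opens consistently with this: "For ITT analyses, all children will be analyzed according to the treatment group to which they were randomized". The same paragraph then adds: "Ineligible children who were erroneously enrolled will be handled as a protocol violation and will be removed from the study, and from the analysis". For what counts as ineligible it points back to the eligibility section. That list includes clinical complications, a failed appetite test and bilateral edema, as well as "Known allergy to any of the ingredients in the RUTF products" and "Caregiver has intention to move out of the study area within the next 6 months".

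Product is handed over at inclusion: staff open the next envelope and "will provide them with the RUTF supplement according to the letter code". Adverse events "will be evaluated at every follow up visit during treatment". SAP Table 5 and the section on sub-group and sensitivity analyses list a single sensitivity analysis, which concerns children switched to standard product near the expiry date. The protocol's Statistical analysis section contains no rule that removes ineligible children.

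**The concern.** An ITT analysis keeps the groups that randomization created. Dropping children afterwards is defensible when the reason was fixed before randomization and is judged the same way in every arm without knowledge of arm or outcome. The SAP states none of these conditions and sets no time limit for the decision.

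The gap matters because some eligibility criteria resemble trial outcomes. A failed appetite test, edema or a clinical complication makes a child ineligible at presentation. Under Transfer to inpatient treatment in SAP Table 1, the same kinds of finding trigger a transfer during treatment. If such a child's enrolment is reviewed only after an early transfer, the SAP does not say which records decide whether the child is a treatment failure or was never eligible. In a non-inferiority trial, losing failures from an intervention arm favours the conclusion being sought.

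The SAP recognizes this hazard elsewhere. Under Statistical methods it warns that excluding switched children from only one arm could distort that arm's results, and it designs the sensitivity analysis to avoid this. The removal of ineligible children gets no comparable care.

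**Working it through.** **1. The texts side by side.** Analysis frame: all participants, by randomized group, with no eligibility exception. Inclusion errors, opening sentence: all children, by randomized group. Inclusion errors, later sentence: ineligible children leave the analysis. A randomized child found to be ineligible cannot satisfy all three. The label modified ITT does not appear, and no planned analysis retains these children.

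**2. Is this a power problem?** First, the plan's own figure. Protocol Table 4 gives 90.0% power with 306 analysed per arm (360 × 0.85), 77% recovery, a 10-point margin and one-sided α = 0.05.

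- Power = Φ(margin/SE − 1.645), with SE = √(2p(1−p)/n).
- SE = √(2 × 0.77 × 0.23/306) = 0.0340. Power = Φ(0.10/0.0340 − 1.645) = 90.2%. The stated figure is reproduced.
- SAP inputs (76% recovery; 12.5% relative margin = 0.125 × 76 = 9.5 points): SE = 0.0345, power = 86.6%.

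Neither document gives an ineligibility rate, so I assume a range of removals:

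| Removed (assumed) | n per arm | Power, protocol inputs | Power, SAP inputs |
|---|---|---|---|
| 0% | 306 | 90.2% | 86.6% |
| 1% | 303 | 90.0% | 86.3% |
| 2% | 300 | 89.7% | 86.0% |
| 5% | 291 | 88.9% | 85.0% |
| 10% | 275 | 87.4% | 83.3% |

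The loss is about 3 points at most. Power is not the issue.

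**3. How large could the bias be?** Let true recovery be p in both arms, let a fraction r of one arm be removed, and let the removed children recover at rate q. Recovery observed in that arm is (p − rq)/(1 − r), so the shift is r(p − q)/(1 − r). Take p = 76% from the SAP; r and q are assumed.

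- r = 5% in one arm, 0% in the other, q = 30%: 0.05 × 0.46/0.95 = 2.4 points. Against the margin: 2.4/9.5 ≈ 0.25.
- r = 2% against 0%, q = 30%: 0.02 × 0.46/0.98 = 0.9 points.
- r = 5% against 2%, q = 30%: 2.42 − 0.94 = 1.5 points.
- r = 5% against 0%, q = 50%: 0.05 × 0.26/0.95 = 1.4 points.
- Equal r in both arms, unrelated to outcome: zero.
- Equal r in both arms, all removed children being failures: each arm's recovery is divided by (1 − r), so the relative risk, which is the SAP's effect measure, does not change.

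Bias in the relative risk therefore needs removals that differ between arms, in number or in the outcomes of those removed. The direction depends on the arm. Losing more failures from an intervention arm favours non-inferiority; losing more from control works against it.

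**4. Safety.** Product is given at inclusion, so a child found ineligible later may already have been exposed. Adverse events are captured at treatment visits, and mortality in SAP Table 1 runs through post-discharge follow-up. The SAP defines no safety analysis set. It says neither that removed children stay in safety follow-up nor that they leave it.

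**The case against.** The strongest defence is that the rule is narrow. It covers children enrolled in error, and the criteria it refers to describe status at presentation. A later reaction, move or complication does not by itself make a child ineligible, and the SAP's missing-data section counts default as a treatment outcome. A reader might infer that removals will be driven by default, transfer or death. The documents do not show that; they only fail to rule it out.

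Investigators and outcome data collectors are blinded and packaging is identical. The SAP's doubt about blinding, on grounds of taste and appearance, concerns participants. This makes differences between arms less likely, but blinding to arm does not stop a decision from being influenced by outcome. The flow diagram will show numbers randomized and analysed, and protocol violations go to the data monitoring board. Removals would thus be visible, but no planned analysis would include the removed children.

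On safety, a reader might infer that adverse-event data for removed children are deleted. No text says so. The protocol provides for routine monitoring and for medical care of adverse events in all study participants, and the procedure for adverse events is in an annex not available here. What stands is the SAP's silence.

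Keeping literally everyone would also go too far, because consent and not being already enrolled are themselves eligibility criteria. Exceptions are needed for children without valid consent and for duplicate enrolment.

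**Conclusion.** The point holds in limited form. The contradiction within the SAP is certain. So is the absence of any requirement for pre-randomization evidence or blinded judgement, and of any analysis retaining the removed children. Whether bias will follow, and how much, cannot be determined from the documents. The illustrations run from zero to 2.4 points; the upper figure rests on assumed one-sided removal of 5% and assumed 30% recovery in those removed, and is not a forecast. For safety, the finding is an unanswered question about children who have received product, not evidence of lost data. The plan should be corrected because the primary conclusion is one of non-inferiority and the remedy is cheap.

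**What to change.** Replace the removal sentence in the SAP's section on inclusion and randomization errors with text to this effect:

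- All randomized children with valid consent stay in the primary ITT analysis in their randomized arm. A child enrolled twice is counted once, by first randomization.
- Ineligible children are excluded only in a sensitivity analysis. It is limited to violations evident from data recorded before randomization and judged blind to arm and outcome.
- Eligibility violations are reported by arm.
- A safety set is defined as all children who received product. Wrongly enrolled children follow the same adverse-event and mortality schedule as other participants, no longer and no shorter.

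Add the new sensitivity analysis to SAP Table 5. The SAP describes late enrolment in the past tense, so the change should be made before any results are examined by arm. If children have already been removed, report their number by arm and the data held on them.

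The cost is SAP wording and one extra analysis. Planned numbers and power do not change. The small downside is that a few children outside the target population remain in the ITT set.

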### Sub-group and sensitivity analyses

We will conduct two *a priori* sub-group analyses for primary study outcomes only. These are for exploratory purposes, and our study did not factor these sub-groups into account in power calculations. We will assess all primary study outcomes separately among the following sub-groups of children:

1. Age group at enrollment: 6-23 months vs 24-59 months
2. Children with high-risk MAM, defined as MAM status at enrollment (defined as above) and any of the following characteristics:
  - a. Age 6-23 months
  - b. WAZ < -3
  - c. MUAC 115-119 mm
  - d. History of SAM
  - e. Present case of MAM is a relapse case

We hypothesize the alternative RUTFs may have a different effect in these sub-groups. First, if the alternative RUTFs impact the gut microbiome of children, these interventions may have greater impact on the anthropometry outcomes of younger children. The gut microbiome before three years of age is especially sensitive to external influences such as nutrition, and thus may represent a critical window in which interventions may have the most influence (32). Conversely, one study on a previous formula of SMS-RUTF reported lower efficacy among children 6-23 months of age (33), although a subsequent study reported non-inferiority of the SMS-RUTF product among this age group after it had been reformulated (19). Further data on the efficacy of this product within the subgroup of 6–23-month-old children is useful.

Children with MAM or SAM have microbiome profiles that are more immature for their age and this deleterious microbiome immaturity is inversely associated with WHZ even within MAM or SAM categories (34). Thus, we hypothesize that children with high-risk MAM may have gut microbiome profiles that are more suboptimal than their lower-risk MAM counterparts, and thus may stand to experience a stronger benefit from any microbiome influences exerted by the products. Additionally, release of new WHO guidelines on the prevention and management of wasting in 2023 recommend prioritize specialized food products (such as RUTF) for high-risk MAM (35), and thus efficacy data within this sub-group may be useful for policymakers in Burkina Faso in implementing these guidelines in the coming years.

As described above, we will conduct one sensitivity analysis, in which we exclude children whose treatment product was switched to the standard RUTF before the expiration date of their treatment product.

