We estimate a total sample size of 1080 children with SAM (360 per arm) and 1080 children with MAM (360 per arm) will provide at least 90% statistical power to demonstrate non-inferiority for each comparison, with a non-inferiority margin of 10 percentage points, assuming a recovery rate in the control of 77% (Table 4). For relapse outcomes, sample size will be smaller, and thus power will be lower, because only recovered children will be included in the analysis. All calculations assume a one-sided $\alpha = 0.05$ for non-inferiority and two-sided $\alpha = 0.05$ for superiority analyses.

Table 4. Sample size calculations

Scenarios with at least 80% power are **bolded**.

Primary outcome	Analysis type	Sample size per arm	Outcome prevalences reported in literature	Non-inferiority margin or detectable effect size	Assumption on control group outcome prevalence/means in sample size calculations	Power per comparison
Anthropometric recovery at discharge	Non-inferiority	360 MAM and 360 SAM children/arm enrolled; 306 MAM and 306 SAM children in analysis after 15% attrition	MAM recovery (with RUSF*): 73% (13); 73% (14); 85% (15) SAM recovery : 55.4% (16); 82.3% (17); 76% (18); 71% (pooled estimate from meta-analysis) (19)	10 percentage points (absolute difference)	55.4% (vs 45.4%)	85.6%
					77.0% (vs 67.0%)	90.0%
					82.3% (vs 72.3%)	96.8%
Relapse to wasting within 3-months post-discharge	Superiority	236 children/arm in analysis (assuming 77% of the 306 children recover)	Post-MAM relapse : 30% within 3 months (period prevalence) (20); 33% within 12-months (21) Post-SAM relapse : 6.8% 3-month cumulative incidence (22); 24% 2-month cumulative incidence (23); 30% within 3-months (unpublished); 2.6 episodes per child-year (unpublished); 1.3	35% relative reduction (incidence rate ratio = 0.65)	Incidence of 2.6 episodes per child-year	80.0%
					Prevalence of 30% (vs 20%)	71.0%

			episodes per child-year (unpublished)			
--	--	--	--	--	--	--

*RUSF = ready-to-use supplementary food

Study procedures

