### Sample size and statistical power

#### Main trial

We estimate a total sample size of 1080 children with SAM (360 per arm) and 1080 children with MAM (360 per arm) will provide sufficient statistical power to demonstrate non-inferiority for each comparison, with a non-inferiority margin of relative 12.5%, assuming a recovery rate in the control of 76% and a loss to follow up of 15% (Table 4). The sample size will be smaller for analyses of relapse, because only recovered children will be included in the analysis. All calculations assume a one-sided  $\alpha = 0.05$  for non-inferiority and two-sided  $\alpha = 0.05$  for superiority analyses,  $\beta = 0.8$ , and 15% attrition. While the key objectives of this research are to evaluate effects of the alternative RUTFs on recovery and relapse, we consider as primary outcomes any outcome for which we have adequate power for clinically or policy meaningful effect sizes (5).

 Stata commands `ssi` for continuous outcomes and `artbin` for binary outcomes were used for non-inferiority analyses, and `power twomeans` for continuous outcomes and `power twoproportions` for binary outcomes were used for superiority analyses. Outcome proportions, means, or standard deviations were taken from relevant studies in literature as delineated in Table 4.

Table 4. Calculations of detectable effect sizes for all outcomes

Outcome	Outcome prevalence in the literature	Type of analysis	Non-inferiority margin (relative) with $\geq 80\%$ power (Non-inferiority)	Detectable effect size at 80% power (Superiority)	Rank of outcome
Anthropometric recovery at discharge	MAM recovery (with RUSF*): 73% (6); 73% (7); 85% (8)  SAM recovery: 55.4% (9); 82.3% (10); 76% (11); 71% (pooled estimate from meta-analysis) (12)	Non-inferiority	12.5% relative margin		Primary
Relapse to wasting within 3-months post-discharge	Post-MAM relapse: 30% within 3 months (13); 33% within 12-months (14)  Post-SAM relapse: 6.8% 3-month cumulative incidence (15); 24% 2-month cumulative incidence (16); 30% within 3-months (unpublished)	Superiority		Risk difference of 11%; Relative risk = 0.72	Primary
Length of stay (LOS) among recovered children	MAM: 36.4 days (SD 50.4 days)(17); 5.9 weeks (95% CI: 4.9, 7.0)(18) SAM: 56 days (assumed 41 day SD) (9)	Non-inferiority	MAM: 4.9 days; 12.5% relative margin SAM: 8 days; 12.5% relative margin		Primary

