## Statistical methods

We will conduct two separate comparisons between (i) the control group and SMS-RUTF, and (ii) between the control group and S-RUTF. All analyses will be done separately by wasting severity status (MAM vs SAM); that is, all analyses will be conducted and presented among MAM children and among SAM children separately. No adjustments for multiple comparisons will be made.

For binary outcomes, we will use log-binomial regression to estimate relative risks (RRs) and 95% confidence intervals (CIs) for the RRs, adjusting for any baseline factors as appropriate (described further below). If the regression model is adjusted, we will present both crude (unadjusted) and adjusted model results. If the models do not converge, we will use Poisson regression models with robust estimation of standard errors (26) and report which model was used. Non-inferiority will be declared if the lower bound of a one-sided 95% CI for the RR lies entirely below the non-inferiority margin of a relative 12.5%. For superiority analyses, we will use a two-sided 95% CI and superiority will be declared if the lower bound of the 95% CI for the relative risk is above 1.0. All analyses will be adjusted for health center to reflect the stratified randomization (27–29).

For continuous outcomes measured at one timepoint, we will use linear regression to estimate differences in that outcome between treatment arms, adjusting for any baseline factors as appropriate and health center (as explained above). Both unadjusted and adjusted model results will be presented.

For any outcome for which non-inferiority is demonstrated, we will then sequentially test for superiority. In these cases, we will report both non-inferiority and superiority results. The superiority analysis will be considered exploratory, as the study power calculations were based on non-inferiority effect size.

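### The SAP hypothesizes that effects differ between subgroups but plans only separate within-subgroup analyses, so that hypothesis is never tested

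*SAP*

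**What the plan says.** The SAP section on sub-group and sensitivity analyses names two factors. The first is "Age group at enrollment: 6-23 months vs 24-59 months". The second is high-risk MAM, defined by any one of five characteristics, the first of which is age 6-23 months. The method is a single sentence: "We will assess all primary study outcomes separately among the following sub-groups of children".

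The same section gives the purpose: "We hypothesize the alternative RUTFs may have a different effect in these sub-groups". The reasons are comparative. Younger children may gain more through the microbiome, although an earlier SMS formulation did worse at that age. Children with high-risk MAM "may have gut microbiome profiles that are more suboptimal than their lower-risk MAM counterparts" and so may benefit more. The section also says that efficacy data within the 6-23 month group and within high-risk MAM are useful in themselves, the latter for policymakers.

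It is open about status: "These are for exploratory purposes, and our study did not factor these sub-groups into account in power calculations". Under Statistical methods, "all analyses will be conducted and presented among MAM children and among SAM children separately", with no adjustment for multiple comparisons.

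**The concern.** A hypothesis that effects differ between groups concerns a contrast of treatment effects. A separate analysis in each group asks whether there is an effect, or non-inferiority, inside that group. Neither the SAP (Statistical methods, Analysis frame, Sub-group and sensitivity analyses) nor the Protocol's Statistical analysis section names an interaction term, a heterogeneity test or a between-subgroup estimate. For high-risk MAM the comparator in the hypothesis, lower-risk MAM, is not listed for analysis.

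At stake is how the results will be read. A product that is non-inferior in one age group and not in the other looks like effect modification, when smaller numbers alone can produce that pattern. The opportunities are many. SAP Table 1 lists 18 primary variables, counting six anthropometric measures at each of two timepoints. With two comparisons and five subgroup cells (two age groups in MAM, two in SAM, and high-risk MAM), that makes 18 × 2 × 5 = 180 subgroup results.

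**Working it through.** **Inputs.**
- Recovery: control 76%, relative margin 12.5% (RR 0.875), 15% loss (SAP, Sample size and statistical power). Analysed per arm per stratum: 360 × 0.85 = 306 (Protocol Table 4).
- Relapse: 306 × 0.77 = 236 per arm, 30% control, 35% relative reduction (Protocol Table 4). The Protocol states 0.65 as an incidence rate ratio; here it is applied as a risk ratio, giving 19.5%.
- Alpha: one-sided 0.05 for non-inferiority, two-sided 0.05 for superiority.
- Assumed: the age split, 50:50 to 80:20.
- Reading: the SAP's two declaration rules are taken in their evident direction, i.e. lower bound above 0.875 for recovery and upper bound below 1.0 for relapse.

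**Step 1. Reproduce the plan's power.** Non-inferiority at 77% with a 10-point margin: Φ(0.10/√(2·0.77·0.23/306) − 1.645) = Φ(0.10/0.0340 − 1.645) = 90.2% (Protocol: 90.0%). Relapse 30% versus 20% at 236 per arm: 71.0% (Protocol: 71.0%).

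**Step 2. Recovery, no true difference in either age group.** SE of log RR = √(2(1−p)/(np)); probability of declaring non-inferiority = Φ(0.1335/SE − 1.645), where 0.1335 = −ln 0.875. With pass probabilities a and b in independent subgroups, the probability of opposite verdicts is a(1−b) + b(1−a).

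| Split | n per arm | a | b | Opposite verdicts |
|---|---|---|---|---|
| 50:50 | 153 / 153 | 0.668 | 0.668 | 44% |
| 70:30 | 214 / 92 | 0.792 | 0.486 | 51% |
| 80:20 | 245 / 61 | 0.837 | 0.371 | 59% |

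Simulation gave 44%, 50% and 58%. On the risk-difference scale the results are 47%, 53% and 60%.

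**Step 3. Relapse, RR 0.65 in both age groups.** SE = √((1−p₁)/(np₁) + (1−p₂)/(np₂)); probability of declaring superiority = Φ(0.4308/SE − 1.96), where 0.4308 = −ln 0.65.

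| Split | n per arm | a | b | Opposite verdicts |
|---|---|---|---|---|
| 50:50 | 118 / 118 | 0.453 | 0.453 | 50% |
| 70:30 | 165 / 71 | 0.586 | 0.297 | 54% |
| 80:20 | 189 / 47 | 0.644 | 0.213 | 58% |

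Using 30% versus 20% instead, at 233 per arm, gives 49% to 57%.

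**Step 4. Where the figure is smaller.**
- Recovery 82.3%: 31%, 40% and 52% over the three splits.
- Recovery 85%: 22%, 32% and 46%.
- Relapse with no effect in either group: 2 × 0.025 × 0.975 = 4.9%, or 2 × 0.05 × 0.95 = 9.5% if either direction counts.
- Discharge MUAC in MAM: the margin is 6.8 mm. An SD of about 10.9 mm follows from the SAP's 2.46 detectable difference, if that is read as mm and 306 per arm is assumed. At 50:50 each group passes more than 99.9% of the time, so discordance is below 1%.

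**Step 5. What an interaction test would do.** With identical effects, a two-sided 5% treatment-by-subgroup test on log RR signalled a difference in 4.5% to 5.0% of simulated trials. Its power is poor. Take recovery RR 0.875 in the smaller group (0.76 × 0.875 = 66.5%) and 1.0 in the other. The SE of the log ratio of RRs is 0.0974 at 50:50 and 0.1264 at 80:20, so power is 28% and 18%.

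**The case against.** The strongest reply is that the SAP labels these analyses exploratory and unpowered, sets no subgroup decision rule, and nowhere says that differing verdicts will be taken as effect modification. That stands. A reader might infer that the SAP plans to conclude effect modification from discordant results; the text does not support this, and the discordance figures describe only what would follow if someone drew that inference. Nor are 44% to 59% and 5% error rates of the same kind: most of the discordance is low power within subgroups.

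It is also fair that the SAP wants efficacy data within the 6-23 month group and within high-risk MAM. Separate estimates serve that aim and should not be dropped.

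The interaction has weaknesses too. Its power is low, so a non-significant result could be misread as equal effects. And because every MAM child aged 6-23 months is high-risk by definition, lower-risk MAM consists only of children aged 24-59 months, so the age and risk contrasts overlap within MAM.

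What the reply does not answer is the mismatch. The exploratory label governs how strongly a result may be claimed, not which question the analysis addresses.

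**Conclusion.** The point holds as a gap between hypothesis and method: the plan states a difference in effects and specifies nothing that estimates or tests one, and for risk status in MAM the comparator is not listed. This depends on no arithmetic.

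The size is conditional. Opposite age-group verdicts under identical effects would arise in about 44% to 59% of trials for recovery and 50% to 58% for relapse, given the design rates, a relapse effect equal to the design effect, and assumed splits. A reader might generalize this to about half the time for any primary outcome. That is not supported: Step 4 shows lower rates at higher recovery and very low ones for a null relapse effect or a wide margin. The figure also has no meaning for high-risk MAM, where no second verdict is planned.

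The main comparisons, their error rates and the sample size are unaffected. This is an inexpensive improvement to a disclosed exploratory analysis.

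**What to change.** In the sub-group section of the SAP:

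- Add treatment × age group to the planned models (with health center) for each primary outcome within MAM and within SAM. Within MAM, also add treatment × risk status, naming lower-risk MAM as the comparator.
- Report the ratio of RRs, or the difference in differences for continuous outcomes, with its 95% CI as the exploratory evidence on effect modification.
- Keep the within-subgroup estimates with CIs, and state that differing within-subgroup verdicts are not evidence of a different effect.
- State that interaction power is low (about 18% to 28% for recovery RR 0.875 versus 1.0), so a non-significant interaction does not show equal effects.
- State that high-risk MAM contains all MAM children aged 6-23 months, so the two interactions overlap and are not independent findings.

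The cost is a few lines of text and one added interaction per model, with no new data. The drawback is wide interaction intervals, which show fairly how little the trial can say about differences between subgroups.
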